### **2.4.5.1 Analyses of hypoglycemia**

Analyses of hypoglycemia will be performed on the TEAE period, as defined in [Section 2.1.4](#). Hypoglycemia will be classified as severe hypoglycemia, documented symptomatic hypoglycemia, asymptomatic hypoglycemia, probable symptomatic hypoglycemia or relative hypoglycemia (see [Section 2.1.4.1](#)).

The number (%) of patients with any hypoglycemia, severe hypoglycemia and documented symptomatic hypoglycemia will be summarized respectively by treatment group for the TEAE period, as well as the incidence rate in patient years. Two types of incidence rates will be presented: the number of patients with at least 1 event per patient years (calculated as the number of patients with at least 1 event / total exposure in patient years), and the number of events per patient years (calculated as the number of events / total exposure in patient years). Note: here exposure is duration of TEAE period, ie, duration of IMP treatment in days +1 (see [Section 2.1.4](#)).

The summary of frequency and incidence rate in patient years for severe hypoglycemia or documented symptomatic hypoglycemia will be provided as appropriate by gender (Male, Female), age group (<50, ≥50 to <65, ≥65 to <75, ≥75 years of age), race (American Indian or Alaska Native, Asian/Oriental, Black, Native Hawaiian or Other Pacific Islander, White, Other).

The summary of frequency and incidence rate in patient years for severe hypoglycemia or documented symptomatic hypoglycemia will be provided as appropriate by anti-SAR425899 antibody status (Positive, Negative) during TEAE period. A patient is defined as anti-SAR425899 antibody positive during the TEAE period if the patient is anti-SAR425899 antibody positive at any time during TEAE period, ie, duration of IMP treatment in days +28 (see [Section 2.1.4](#)).

A KM curve will also be provided by treatment group for the time to first onset of severe or documented symptomatic hypoglycemia during the TEAE period.

A listing of patients for all hypoglycemic events reported on the dedicated eDiary or eCRF “Hypoglycemic Event Information” form will be provided with each category flagged (ie, severe hypoglycemia, documented symptomatic hypoglycemia, asymptomatic hypoglycemia, probable symptomatic hypoglycemia and relative hypoglycemia).

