4 INTRODUCTION AND RATIONALE

Glucagon-like peptide-1 (GLP-1) is an endogenous enteroendocrine hormone secreted by L-cells of the distal intestine in response to oral nutrient ingestion. Glucagon-like peptide-1 has multiple physiologic effects that contribute to ameliorating hyperglycemia in the treatment of type-2 diabetes mellitus (T2DM). These effects include enhancing insulin secretion from pancreatic β -cells in a glucose dependent manner, suppressing glucagon secretion, and slowing gastric emptying (1). Glucagon-like peptide-1 also enhances satiety with subsequent reduction in food intake thereby promoting weight loss. About 80% of patients with T2DM are overweight or obese. Many of the available classes of treatment options for T2DM (eg, sulfonylureas, glinides, thiazolidenediones, and insulin) are actually associated with promoting weight gain, a distressing side effect for patients already struggling with excess body weight and one that may adversely impact adherence to therapy (2). In recent years, a new class of pharmacotherapy for T2DM has emerged in the form of GLP-1 receptor agonists, which are notable for promoting modest weight loss in addition to having insulinotropic actions and glycemetic efficacy.

Another enteroendocrine hormone that has gained interest as a potential therapeutic option for the treatment of obesity/T2DM is oxyntomodulin (OXM). Like GLP-1, OXM is secreted by L-cells of the distal gut and is also derived from the same precursor peptide proglucagon.

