8.8.2 Rescue therapy

In case of FPG or HbA1c above pre-defined thresholds and if no reasons can be found for insufficient glucose control, it is recommended to add rescue therapy.

Central laboratory alerts on FPG and HbA1c are set up to ensure that glycemic parameters remain under predefined threshold values (see hereinafter).

The threshold values are defined as follows, depending on study period:

From baseline Visit 4 (Week 0) to Visit 9 (Week 8, including value at Visit 9): FPG >270 mg/dL (15.0 mmol/L).

From Visit 9 (Week 8) to Visit 10 (Week 14): FPG > 240 mg/dL (13.3 mmol/L).

From Visit 10 (Week 14) to Visit 12 (Week 26): FPG>200 mg/dL (11.1 mmol/L) or HbA1c>8%.

In case of FPG / HbA1c above the threshold values, the investigator should ensure that no reasonable explanation exists for insufficient glucose control, and in particular that:

- Plasma glucose was actually measured in fasting condition (ie, after at least 8 hrs fast).
- Investigational product is given at planned dose.

- There is no intercurrent disease, which may jeopardize glycemic control (eg, infectious disease).
- Compliance with treatment is appropriate.
- Compliance with diet and lifestyle is appropriate.

If any of the above can reasonably explain the insufficient glycemic control, the investigator should undertake appropriate action, ie,

- Dose increase of investigational product according to protocol (if tolerance allows).
- Set up adequate investigation and treatment of intercurrent disease (to be reported in AE/concomitant medication parts of the eCRF).
- Stress on the absolute need to be compliant with treatment.
- Organize a specific interview with a Registered Dietician or other qualified nutrition professional and stress on the absolute need to be compliant to diet and lifestyle recommendations, and check a FPG / HbA1c assessment at the next visit.

If none from the above-mentioned reasons can be found, or if appropriate action fails to decrease FPG / HbA1c under the threshold values, rescue medication may be introduced.

The choice of rescue therapy is at the investigator's discretion with the exception of using GLP-1 receptor agonists or DPP4 inhibitors.

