All assessments planned in Visit 12 are to be performed before initiating rescue therapy. After these assessments are completed and rescue therapy initiated, the patient will remain in the study and continue to administer the study treatment (including background therapy). The planned visits and assessments should be performed until the last scheduled visit.

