9.2.2.1 Observation period of safety endpoints

The observation period of safety data will be divided into 3 segments:

- The pretreatment period is defined as the time between the date of the informed consent and the first injection of IMP.
- The on-treatment period is defined as the time from the first injection of IMP up to 3 days (1 day for hypoglycemia) after the last injection of IMP, regardless of the introduction of rescue therapy. The 3-day interval is chosen based on the half-life of the IMP (approximately 5 times the half-life of SAR425899).
- The post treatment period is defined as the time starting 4 days after last injection of IMP (after the on-treatment period).

The baseline value for safety endpoints will be the last available value prior to the first injection of IMP.

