11.4.3.1 Analyses of hypoglycemia

The number (%) of patients and rate in patient years (2 types: the number of patients with events or the total number of events per 100 patient-year) of each type of hypoglycemia (severe, documented, asymptomatic, probable and relative hypoglycemia) will be summarized by treatment group. The pattern of symptomatic hypoglycemia occurrence over time will also be assessed, as appropriate. An overall hypoglycemia (includes severe, documented, asymptomatic, probable and relative) table will also be provided.

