For percentage of patients requiring rescue therapy, patients who have received rescue therapy during the 26-week treatment period will be summarized.

For HbA1c and body weight responders, a sensitivity analysis will be performed treating patients as non-responders if they receive rescue therapy, or have no measurement at Week 26. The sensitivity analysis includes measurement at Week 26, regardless of treatment discontinuation.

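### Hypoglycemia is counted through rescue therapy, which may include insulin or a sulfonylurea; a pre-rescue table and a rescue flag in the listing would be a cheap supplement

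*SAP*

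**What the plan says.** **Window.** SAP 2.4.5.1 states: "Analyses of hypoglycemia will be performed on the TEAE period". SAP 2.1.4 defines that period by study-drug administration only. Protocol 9.2.2.1 is explicit about rescue: "1 day for hypoglycemia) after the last injection of IMP, regardless of the introduction of rescue therapy". The exposure denominator in SAP 2.4.5.1 is treatment duration plus one day, also without a cut at rescue.

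**Outputs.** SAP 2.4.5.1 plans numbers and percentages, two incidence rates, breakdowns by gender, age, race and antibody status, and a listing flagged by event category. It adds: "A KM curve will also be provided by treatment group for the time to first onset of severe or documented symptomatic hypoglycemia". Protocol 11.4.3.1 says: "The pattern of symptomatic hypoglycemia occurrence over time will also be assessed, as appropriate". None of these is cut at rescue or identifies events by rescue status. SAP Appendix B, the summary of analyses, is not in the supplied text.

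**Rescue.** Under Protocol 8.8.2, after rescue starts, "the patient will remain in the study and continue to administer the study treatment". The investigator chooses the drug, "with the exception of using GLP-1 receptor agonists or DPP4 inhibitors". The Protocol's introduction names "sulfonylureas, glinides, thiazolidenediones, and insulin" among available drug classes. It does so when discussing weight gain, so it shows only that such drugs exist and not what investigators would choose.

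**Rescue elsewhere in the SAP.** For HbA1c and body weight responders, SAP 2.4.4.2 says "a sensitivity analysis will be performed treating patients as non-responders if they receive rescue therapy". There is no counterpart for hypoglycemia.

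**The concern.** Hypoglycemia is a named safety endpoint. If a rescued patient has an event while taking both study drug and, say, insulin, the planned tables cannot show which treatment regimen it belongs to.

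Rescue is likely to be unequal if SAR425899 works. Entry HbA1c runs from 7.0% to 10.0%, one randomization stratum is 8% or above, and from Week 14 an HbA1c above 8% is a rescue threshold. A placebo patient who enters above 8% and does not improve reaches it. The percentage needing rescue is itself a secondary efficacy endpoint. More placebo rescue with hypoglycemia-inducing drugs would add events mainly to a group of 30 patients and make SAR425899 look relatively safer. At stake is how clearly the report describes hypoglycemia on study drug without rescue.

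**Working it through.** **Plan's own figure.** The hypoglycemia section states none. The group sizes come from the sample-size section (Protocol 11.1), whose 80% power reproduces: 0.7 / [1.1 × √(1/30 + 1/60)] = 2.85, giving 81.2% by the normal approximation and 80.4% by noncentral t. This point does not alter it.

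**Inputs from the documents.** 60 patients per SAR425899 arm, 30 pooled placebo, 26 weeks of treatment: 30 and 15 patient-years if all complete.

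**Assumed inputs.** The documents give no rescue or event rates. I assume base rates of 0.2 (SAR425899) and 0.1 (placebo) events per patient-year, that is 6 and 1.5 expected events. I also assume constant hazards, no dropout, the same added rate in both arms, and that insulin or a sulfonylurea raises hypoglycemia risk.

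**Formulas.**
- Post-rescue patient-years = N × fraction rescued × weeks / 52.
- Extra events = post-rescue patient-years × share on a hypoglycemia-inducing drug × added rate.
- Group rate = base rate + extra events / total patient-years.

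**One case in full** (5% v 30% rescued, 6 weeks, all on such a drug, 1 added event per patient-year):
- Placebo: 30 × 0.30 × 6/52 = 1.04 patient-years, so 1.04 extra events; rate 0.1 + 1.04/15 = 0.169.
- SAR425899: 60 × 0.05 × 6/52 = 0.35 patient-years, so 0.35 extra events; rate 0.2 + 0.35/30 = 0.212.
- The difference falls from 0.10 to 0.042 per patient-year.

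| Rescued, SAR425899 v placebo | Weeks after rescue | Share on such a drug | Added rate | Extra SAR425899 events | Extra placebo events | Rate difference (0.10 without rescue effect) |
|---|---|---|---|---|---|---|
| 2% v 5% | 6 | half | 0.5 | 0.03 | 0.04 | 0.098 |
| 5% v 15% | 9 | half | 1 | 0.26 | 0.39 | 0.083 |
| 5% v 20% | 6 | all | 0.5 / 1 / 2 | 0.17 / 0.35 / 0.69 | 0.35 / 0.69 / 1.38 | 0.083 / 0.065 / 0.031 |
| 5% v 30% | 6 | all | 0.5 / 1 / 2 | 0.17 / 0.35 / 0.69 | 0.52 / 1.04 / 2.08 | 0.071 / 0.042 / −0.015 |
| 5% v 30% (extreme) | 12 | all | 2 | 1.38 | 4.15 | −0.131 |

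If only half of rescued patients receive such a drug, the extra placebo events in the 20% and 30% six-week rows halve to 0.17 / 0.35 / 0.69 and 0.26 / 0.52 / 1.04.

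**Patients with an event** (5% v 30%, six weeks, all on such a drug): 9.5% v 4.9% without rescue effect becomes 9.8% v 6.5%, 10.0% v 8.0% and 10.4% v 10.8% for the three added rates.

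**Early part of the KM curve.** Before Week 14 only fasting glucose above 270 mg/dL, then 240 mg/dL, triggers rescue, so early curves are little affected. With rescue confined to the last six weeks, the curve to Week 20 is unchanged: 1 − exp(−0.2 × 20/52) = 7.4% and 1 − exp(−0.1 × 20/52) = 3.8%.

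**Direction.** With equal proportions rescued and equal added risk the difference stays at 0.10. The shift reverses if rescue adds more risk on SAR425899 than on placebo by a factor above the ratio of placebo to SAR425899 rescue proportions: 30/5 = 6, or 20/5 = 4.

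**Precision.** 0.10 ± 1.96 × √(1.5/15² + 6/30²) = about −0.13 to 0.33 per patient-year.

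**Exposure lost by cutting** (5% v 30%, six weeks): 0.30 × 6/26 = 6.9% of placebo and 0.05 × 6/26 = 1.2% of SAR425899 patient-time.

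**The case against.** The strongest reply is that the window is deliberate. The Protocol says outright that rescue does not end it, and SAP 2.5.4 treats last on-treatment safety values the same way. SAP 2.4.5 calls safety analysis essentially descriptive. Rescue is discretionary and comes only after other explanations or corrective action, so 30% on placebo is a high assumption. Rescue use is already compared by arm, concomitant medications are tabulated by therapeutic class, and every hypoglycemic event is listed. The responder sensitivity analysis is no real precedent, because there rescue helps produce the efficacy outcome. With perhaps one affected event, a listing flag might be enough.

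Most of this stands. It limits the point to a supplement and argues for a small one. What it leaves open is that no planned output in the supplied text links an event to rescue status, although the eCRF records rescue.

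Three stronger readings are tempting and not supported:
- **That the through-rescue table is wrong.** It describes hypoglycemia under the treatment policy as given, which is a proper main summary.
- **That rescue is a confounder that a cut would remove.** Rescue occurs after randomization and partly as a result of treatment; it is an intercurrent event. Cutting there exchanges post-rescue events for informative censoring.
- **That one or two extra placebo events should be expected.** The documents contain no rates, and many of the cases above fall below one.

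**Conclusion.** The point holds as a modest improvement to consider. The planned hypoglycemia summaries include post-rescue events and exposure, and the supplied text offers no pre-rescue view. The plausible cases give from 0.04 to about 2 extra placebo events; about 4 requires 30% of placebo rescued at Week 14, all on hypoglycemia-inducing drugs at a high added rate. The likely direction favors SAR425899, provided placebo patients are rescued more often and the added risk is not several times greater on SAR425899. These shifts are small against a confidence interval of about −0.13 to 0.33 per patient-year, so neither table could resolve them. Efficacy, power and type I error are untouched. All rates are assumptions, and the absence of a pre-rescue summary is subject to SAP Appendix B.

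**What to change.** In SAP 2.4.5.1:
- Keep the table on the treatment-emergent period as the main summary.
- Flag events after rescue start in the hypoglycemia listing.
- Add one supplementary descriptive table with n (%) and events per patient-year for any, severe and documented symptomatic hypoglycemia. Cut events and exposure at the earlier of the day before rescue start and one day after the last injection. A rescue-cut KM curve is optional.
- State a rule for partial or missing rescue dates, because SAP 2.5.3 imputes no medication dates. One option is the earliest date the record allows, but not before the visit preceding the one at which rescue was reported. Where a pre-rescue visit is recorded (SAP 2.5.4), its date gives a firmer lower limit.
- Present both tables side by side and treat the cut table as supportive only.

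The cost is SAP wording, one table and one listing flag; SAP 2.5.8 shows that rescue is already captured on two eCRF pages. The downsides are slightly less exposure, possible loss of some true pre-rescue time when a partial date is set early, and informative censoring, because the most hyperglycemic patients leave the risk set.

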9.2.2 Safety endpoints

The following safety parameters will be analyzed:

- AEs, serious adverse events (SAEs) and adverse events of special interests (AESIs).
- Hypoglycemia (severe, documented, asymptomatic, probable, relative).
- Safety laboratory values.
- Vital signs and physical examination.
- Electrocardiogram (ECG) changes.
- Change of heart rate from baseline to Week 26 by ECG.
- Change of heart rate from baseline to Week 26 by Holter monitor in up to 50% subset of all patients.
- Immunogenicity (anti-SAR425899 antibodies).

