### **Probable symptomatic hypoglycemia**

Probable symptomatic hypoglycemia is an event during which symptoms of hypoglycemia are not accompanied by a plasma glucose determination, but was presumably caused by a plasma glucose concentration less than or equal to 70 mg/dL (3.9 mmol/L); symptoms treated with oral carbohydrate without a test of plasma glucose.

In the eCRF, probable symptomatic hypoglycemia is identified based on information captured in the “Symptomatic hypoglycemic event information” page as those

- not ticked “Subject was Not Capable of Treating Self and Required Assistance” to the question “Countermeasure Administration” and
- ticked “Yes” to the question “Were Symptoms Present” and
- ticked “Yes” to the question “Was Any Countermeasure Given for the Hypoglycemic Event?” and
- ticked “Yes” to the question “Did this countermeasure lead a significant improvement or prompt recovery?” and
- with no plasma glucose value before countermeasure.

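### SAP 2.4.5.1 plans no by-group counts or rates for asymptomatic, probable symptomatic and relative hypoglycemia, which protocol 11.4.3.1 requires

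*SAP*

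**What the plan says.** Protocol 11.4.3.1 states that the number and percentage of patients, and two rates per patient-time (patients with events, and total events), "of each type of hypoglycemia (severe, documented, asymptomatic, probable and relative hypoglycemia) will be summarized by treatment group". It then adds a pooled summary: "An overall hypoglycemia (includes severe, documented, asymptomatic, probable and relative) table will also be provided". The overall table therefore comes on top of the by-type results and does not replace them.

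SAP 2.4.5.1 begins with the same five types: "Hypoglycemia will be classified as severe hypoglycemia, documented symptomatic hypoglycemia, asymptomatic hypoglycemia, probable symptomatic hypoglycemia or relative hypoglycemia". The by-group summary that follows is narrower: "The number (%) of patients with any hypoglycemia, severe hypoglycemia and documented symptomatic hypoglycemia will be summarized respectively by treatment group". Both incidence rates are attached to those three rows. The subgroup, antibody-status and Kaplan-Meier analyses in the section use severe or documented symptomatic events only. The section closes with a listing of all hypoglycemic events, which "will be provided with each category flagged (ie, severe hypoglycemia, documented symptomatic hypoglycemia, asymptomatic hypoglycemia, probable symptomatic hypoglycemia and relative hypoglycemia".

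Protocol 9.2.2 and SAP 2.1.4 both name all five types as safety endpoints. SAP 1.6 says that its Table 2 gives the major changes to the analysis, and that table has no entry on hypoglycemia.

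**The concern.** The types pooled in the any-hypoglycemia row carry very different evidential weight. Under SAP 2.1.4.1, an asymptomatic event has a measured glucose at or below 70 mg/dL. A probable symptomatic event is one "with no plasma glucose value before countermeasure". A relative event has a measured glucose above 70 mg/dL, and the eCRF rule sets no upper limit.

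Probable and relative events depend on symptoms reported by the patient. Liraglutide is open-label, and the dose level of SAR425899 or placebo is not blinded (protocol 6.1 and 8.3.1). Symptom reporting could therefore differ between arms without any difference in measured low glucose. A by-type table is how a reader of the study report would check this. Without it, an imbalance in the any-hypoglycemia row has no breakdown beyond severe and documented events, and three named safety endpoints have no by-group result.

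**Working it through.** The plan states no figure to reproduce, and the point rests on no power, alpha or event-rate assumption. The check compares the two texts and then asks what the planned tables can identify.

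**Step 1. Required against planned by-group summaries (n, %, both rates).**

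| Type | Protocol 11.4.3.1 | SAP 2.4.5.1 table | SAP 2.4.5.1 listing |
|---|---|---|---|
| Severe | yes | yes | flagged |
| Documented symptomatic | yes | yes | flagged |
| Asymptomatic | yes | no | flagged |
| Probable symptomatic | yes | no | flagged |
| Relative | yes | no | flagged |
| Overall / any | yes | yes | not applicable |

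Two of the five types are tabulated, so 5 − 2 = 3 are not.

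**Step 2. Can the missing rows be obtained from the planned ones?** The eCRF rules in SAP 2.1.4.1 make the types mutually exclusive for a single event. Severe requires the assistance box to be ticked and the other four require it not to be. Those four are then separated by presence of symptoms and by glucose at or below 70 mg/dL, above 70 mg/dL, or absent. Event counts can therefore be subtracted:

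residual = any − severe − documented = asymptomatic + probable + relative (+ unclassified)

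That is one equation with at least three unknowns. With assumed counts, for illustration only, of 20 events in all, 1 severe and 7 documented, the residual is 20 − 1 − 7 = 12. Ignoring unclassified events, 12 events can be divided among three types in C(14, 2) = 14 × 13 / 2 = 91 ways. The tables do not say which.

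Patient counts cannot be subtracted even to this extent, because one patient can have events of several types.

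**Step 3. What any hypoglycemia contains.** SAP 2.4.5.1 does not define it. The protocol's overall table, which pools all five types, is the nearest definition and is assumed here. A symptomatic event with no glucose value and no countermeasure meets none of the five eCRF rules, so the total may also hold unclassified events.

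**Step 4. What the listing supplies.** Each event is flagged by category, so events of each type can be counted by hand or from the derived data. The listing does not itself present by-group n, % or exposure-based rates.

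**The case against.** A reader might infer that the any-hypoglycemia total cannot be separated at all, or that the events outside the severe and documented rows have no stated nature. The documents do not support that. SAP 2.4.5.1 classifies every event and plans a listing with all five categories flagged, so the split can be recovered. Nor is the residual wholly unconfirmed, since asymptomatic events within it have a measured glucose at or below 70 mg/dL.

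Four further objections carry weight.

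- Safety analysis is descriptive, with no systematic testing planned (SAP 2.4.5). Severe and documented symptomatic events, which the further analyses use, keep their own rows and cannot be obscured by the pooled one.
- Table 2 covers major changes, and whether three descriptive rows are major is arguable. The SAP does not say that the other types will go unsummarized, so this may be incomplete drafting rather than a decision. On the other side, Table 2 does record a revised definition of treatment compliance.
- SAP Appendix B, the summary of statistical analyses, was not available, and a by-type table there can be neither confirmed nor excluded.
- No figure in the documents gives the size of any effect on the safety results.

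These points limit the consequence. They do not remove the mismatch: the protocol promises by-group counts and rates for every type, SAP 2.4.5.1 specifies them for two types and the total, and a listing is not a by-group summary.

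**Conclusion.** The point holds as a minor inconsistency between protocol and SAP. Followed as written, SAP 2.4.5.1 gives three of the five protocol-defined types no by-group count, percentage or rate, although SAP 2.1.4 names them as safety endpoints and no change is recorded. The planned summary tables cannot divide any hypoglycemia into its measured asymptomatic, unmeasured and above-70 mg/dL parts, although the flagged listing preserves the information. No efficacy conclusion or test is affected.

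This rests on two assumptions: that any hypoglycemia pools all five types, as the protocol's overall table does, and that Appendix B contains no by-type table.

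**What to change.** In SAP 2.4.5.1, add asymptomatic, probable symptomatic and relative hypoglycemia to the by-group table with the statistics already planned for the other rows: number and percentage of patients, and both incidence rates. Check that Appendix B agrees.

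The cost is three rows in an existing table, from flags already derived for the listing. No new data or derivation is needed.

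If the narrower table was intended, the alternative is to record and justify it in SAP Table 2. That would settle the inconsistency but would still leave three named endpoints without a by-group result, so adding the rows is preferable.

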6.2 DURATION OF STUDY PARTICIPATION

6.2.1 Duration of study participation for each patient

The study comprises 3 periods as described below (please see the graphical study design and study flowchart in [Section 1.1](#) and [Section 1.2](#), respectively):

- A 3-week screening period,
- A 26-week treatment period,
- And a 3-day post treatment follow-up period.

The total duration of the study will be approximately 30 weeks for each patient.

A detailed description of the assessments performed in each study period is provided in [Section 10.1](#).

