# 1 OVERVIEW AND INVESTIGATIONAL PLAN

## 1.1 STUDY DESIGN AND RANDOMIZATION

This is a multicenter, multinational, randomized, placebo-controlled, 7-arm parallel-group Phase 2 study. The study is double-blind with regard to SAR425899 and placebo treatments. It is open-label with regard to liraglutide comparative treatment. The volume of investigational medicinal product (IMP; ie, dose of SAR425899 or matching placebo) is not blinded.

Patients will be randomized into 1 of the 7 treatment arms:

- 3 SAR425899 treatment arms receiving 3 dose levels (60 patients per arm).
- 3 corresponding SAR425899 placebo treatment arms receiving 3 dose levels (10 patients per arm, 30 patients total).
- 1 active comparator arm receiving 1.8 mg liraglutide (60 patients).

For the biostatistical analyses, data from the 3 SAR425899 placebo arms will be pooled into 1 placebo group.

Patients will be stratified by screening visit HbA1c (<8% versus ≥8%) and Visit 4 (Day 1) body mass index (BMI: <35.0 kg/m^2 versus ≥35.0 kg/m^2).

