#### *Observation period*

The observation period will be divided into 4 epochs:

- The **screening** epoch is defined as the time from the signed informed consent date up to the first administration of the IMP.
- The **treatment** epoch is defined as the time from the first administration of the IMP to the last administration of the IMP
- The **residual treatment** epoch is defined as the time from the last administration of the IMP up to 3 days (1 day for hypoglycemia, 28 days for anti-SAR425899 antibody) after the last administration of IMP.

The treatment-emergent adverse event (TEAE) period will include both **treatment** and **residual treatment** epochs.

- The **posttreatment** epoch is defined as the period of time starting the day after the end of the treatment-emergent adverse event period up to the end of the study (defined as last protocol-planned visit or the resolution/stabilization of all serious adverse events (SAE) and adverse events with prespecified monitoring as defined in protocol).

The on-study observation period is defined as the time from the start of treatment until the end of study (defined as the last scheduled visit for those who completed the study and the date collected on e-CRF page “Completion of End of Study/Follow-up” for those who did not complete the study, or the resolution/stabilization of all serious adverse events and adverse events with prespecified monitoring as defined in the protocol whichever is the latest).

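### The patient-level hypoglycemia rate keeps exposure after the first event in its denominator, so it lies at or below the rate per patient-year at risk of a first event

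*SAP*

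**What the plan says.** SAP 2.4.5.1 presents, for any, severe and documented symptomatic hypoglycemia, the count and percentage of patients and two figures that it calls incidence rates. The patient-level figure is "calculated as the number of patients with at least 1 event / total exposure in patient years". The event-level figure is "the number of events per patient years (calculated as the number of events / total exposure in patient years". One note fixes the denominator for both: "here exposure is duration of TEAE period, ie, duration of IMP treatment in days +1". The extra day matches the residual-treatment epoch in SAP 2.1.4 ("1 day for hypoglycemia, 28 days for anti-SAR425899 antibody"). Nothing ends a patient's contribution at the first event.

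Protocol 11.4.3.1 names the same pair ("the number of patients with events or the total number of events per 100 patient-year") but does not define the denominator, so the SAP formula governs.

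SAP 2.4.5.1 also repeats the frequency and rates by sex, age group, race and anti-drug antibody status for severe or documented symptomatic events, and adds one time-to-event display: "A KM curve will also be provided by treatment group for the time to first onset of severe or documented symptomatic hypoglycemia". Safety analyses are descriptive, without systematic testing (SAP 2.4.5).

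**The concern.** An incidence rate of patients with an event should count only the time in which a patient could still have a first event. Here a patient enters the numerator once and stays in the denominator to the end of treatment. Protocol 10.3 asks that study drug be continued where possible, so exposure will usually go on after a hypoglycemic event. Total exposure suits the event-level rate, where repeat events count. It does not suit a figure presented as the incidence of a first event.

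At stake is how a safety table comparing three doses, placebo and liraglutide is read. The understatement runs in one direction only. It also differs between arms when the arms differ in how many patients have an event or how early.

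**Working it through.** **Plan's own figure.** The documents state no hypoglycemia proportion, count or rate, so there is nothing to reproduce. All values of p below are assumptions, shown as a range.

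**Inputs.** Follow-up: "A 26-week treatment period" (Protocol 6.2.1), so 26 × 7 = 182 days, plus 1 day = 183 days; T = 183/365.25 = 0.501 year. Arm size: "3 SAR425899 treatment arms receiving 3 dose levels (60 patients per arm" (SAP 1.1); pooled placebo 30.

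**General formula, equal follow-up.** Take N patients followed for T, a share p with an event, and first events at a mean fraction f of follow-up.

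- Planned rate = pN/(NT) = p/T.
- Time at risk of a first event = (1-p)NT + pN·fT = NT[1 - p(1-f)].
- First-event rate = p/(T[1 - p(1-f)]).
- Planned ÷ first-event rate = 1 - p(1-f), so the shortfall is p(1-f), which is never negative.

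**Constant hazard, full follow-up.** First-event rate = -ln(1-p)/T, so the ratio is p/(-ln(1-p)).

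| Assumed p | Planned, per 100 patient-years | First-event rate, per 100 patient-years | Shortfall |
|---|---|---|---|
| 2% | 3.99 | 4.03 | 1.0% |
| 5% | 9.98 | 10.24 | 2.5% |
| 10% | 19.96 | 21.03 | 5.1% |
| 20% | 39.92 | 44.54 | 10.4% |
| 30% | 59.88 | 71.19 | 15.9% |
| 40% | 79.84 | 101.96 | 21.7% |

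**Timing.** At p = 20% the shortfall is 0.20 × 0.9 = 18% if first events come at 10% of follow-up, 0.20 × 0.5 = 10% at mid-follow-up, and 0.20 × 0.1 = 2% at 90%.

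**Patients, not events.** In an arm of 60 with first events at mid-follow-up, 3 patients with 30 events in all give 0.05 × 0.5 = 2.5%. Twelve patients with one event each give 0.20 × 0.5 = 10%. The arm with more events has the smaller shortfall.

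**Between-arm ratios.** Under a constant hazard, 30% v 10% gives a planned ratio of 0.30/0.10 = 3.0 against ln(0.7)/ln(0.9) = 3.39. For 20% v 5% the figures are 4.00 and 4.35. Movement towards 1 is not guaranteed. If the 20% arm has its first events at 90% of follow-up (shortfall 2%) and the 5% arm at 10% (shortfall 0.05 × 0.9 = 4.5%), the first-event rate ratio is 4.00 × 0.955/0.98 = 3.90, below the planned 4.00.

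**The case against.** The SAP states numerator and denominator in full, and patients with an event per total exposure is a legitimate exposure-adjusted summary. With equal follow-up its between-arm ratio is simply the risk ratio. A reader might infer that 3.0 is wrong and 3.4 is the truth. It is not: 3.0 is a correct risk ratio, and 3.4 is a first-event rate ratio under an assumed constant hazard. This part of the objection stands. What remains is that the SAP calls the figure an incidence rate.

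A reader might also infer that understatement is worst wherever most events occur. The formula does not support that, because repeat events play no part and late first events reduce the shortfall.

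The size may well be small. Background therapy is diet and exercise and/or metformin, and other glucose-lowering agents are excluded (Protocol 7.2.1, E 06), so low proportions are plausible for severe or documented symptomatic events. At p of 5% or less, the constant-hazard shortfall is 2.5% or less. On the other hand, any hypoglycemia includes relative hypoglycemia, which SAP 2.1.4.1 derives from symptoms with glucose above 70 mg/dL and no upper limit, so p could be higher there.

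Precision is also poor. For 18/60 v 3/30 the standard error of the log risk ratio is √(1/18 - 1/60 + 1/3 - 1/30) = 0.582, giving 3.0 with a 95% interval of about 0.96 to 9.4. A move from 3.0 to 3.4 would not change how such a table is read.

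Finally, other displays cover part of the gap. The Kaplan-Meier curve handles time to first event properly, but only for the severe-or-documented composite by arm. It does not cover any hypoglycemia, each category separately, or the subgroup and antibody-status tables. The percentage of patients carries no timing information, and with full equal follow-up the planned rate is only that percentage divided by 0.501 year.

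**Conclusion.** The point holds as a minor one of definition and labelling. The direction is certain, because time at risk of a first event cannot exceed total exposure. The size is not known from the documents: it depends on how many patients have an event and how early, and the 1% to 22% range rests on assumed proportions of 2% to 40%, a constant hazard and full equal follow-up. Where a patient stops study drug at the event, almost no later time accrues and the shortfall for that patient nearly disappears.

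Nothing here supports a wider inference that the safety evaluation is unsound. The effect is confined to descriptive tables. The primary analysis and type I error control are also untouched.

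**What to change.** For the patient-level rate, divide patients with an event by the sum of time from first injection to first event, or to the end of the treatment-emergent period if there is none. Do this separately for any, severe and documented symptomatic hypoglycemia, and in the subgroup and antibody-status tables. Keep total exposure for the all-events rate. If the present formula is kept, at least label it as patients with an event per total exposure, not as an incidence rate.

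No new data are needed, but there is some work. A first-event time must be derived for each category, because the Kaplan-Meier curve supplies only the composite. A rule for partial onset dates is needed too, since SAP 2.5.3 imputes them only to classify events by period. Reported patient-level rates will come out slightly higher than under the planned formula.
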